## 4.0 Study Endpoints (if applicable)

**Primary Endpoint:** The primary endpoint will be determined in Specific Aim 1, the baseline to post intervention feasibility of the e-learning + therapy program. Outcome measures will include baseline to post intervention changes in participant scores on assessments of health literacy and technological literacy as well as their overall qualitative experiences.

## 5.0 Inclusion and Exclusion Criteria/ Study Population

**Inclusion Criteria:** (1) paresis of one arm/hand because of ischemic or hemorrhagic stroke >2 mo. and <3 yrs prior; (2) moderate arm impairment defined as a baseline Fugl-Meyer Assessment of the Upper Extremity score of at least  $32\pm 2$  points but no more than  $47\pm 2$  points (out of 60 points) based on published impairment categories; (3) Montreal Cognitive Assessment score  $\geq 22$  to assure that the cognitive capacity to benefit from this learning-based intervention; (4) the ability to read English; (5) the ability to communicate as per the therapists’ judgement at baseline testing; (6) are 21-90 years of age; (7) have a wi-fi connection in the home and either a computer, smartphone or tablet.

**Exclusion criteria:** (1) lesion or injury to brainstem or cerebellum because lesions in these locations may interfere with learning; (2) other neurological disease that may impair motor or learning skills (e.g., Parkinson’s Disease); (3) pain interfering with reaching; (4) uncorrected vision making it difficult to read information on a computer, tablet or phone.

## 6.0 Number of Subjects

N=12

## 7.0 Setting

All in-person testing, and therapy research activities will occur in [name] College of Health Professions upper extremity motor function research laboratory located in the CHP Research Building at [name]. [name] research laboratory is in the same building as the other research laboratories in the MUSC NIH Center of Biomedical

Research Excellence (COBRE) in Stroke Recovery. The e-learning course will occur on the MUSC MoodleCE Learning Management System.

## **8.0 Recruitment Methods**

Participants with stroke will be recruited from the MUSC NIH Center for Biomedical Research Excellence (COBRE) in Stroke Recovery stroke research recruitment registry called RESTORE (approved MUSC IRB #37803). The Registry currently contains the contact information for ~800 individuals with stroke who have provided consent to be contacted for potential participation in research studies. Importantly, the Center supports a dedicated project coordinator who enrolls 5-10 new participants into the registry per month and supports information technology resources needed to maintain/update the Registry's infrastructure as needed.

## **9.0 Consent Process**

The study project coordinator will work closely with the COBRE in Stroke Recovery's recruitment core. The study project coordinator will query the COBRE research registry according to the inclusion criteria for the present proposal. He will identify potential participants that meet inclusion criteria and inform the PI, Co-I, or study therapist who will contact participants by phone to determine if they want to participate in the current study. If they wish to participate they will be scheduled for a time for the PI, Co-I, research therapist or project coordinator to obtain informed consent for the study proposed. Consent will be obtained after reviewing the protocol and consent form with each potential subject. If a potential subject is deemed unable to participate in informed consent as per the judgement of the PI, co-I, study therapist or project coordinator, consent will be obtained from a legally authorized representative with the patient present. For patients consenting themselves, every attempt will be made to have a relative present during the informed consent. All recruitment and informed consent procedures will be approved by the MUSC IRB.

## **10.0 Study Design / Methods**

**Study Design:** This is a longitudinal cohort design.

**Research Methods:** All study procedures are for research purposes, that is, there are no non-research evaluations or interventions.

**Intervention Methods and Location:** The e-learning and stroke rehabilitation therapy intervention to be studied is described above in section 3.0. All in-person procedures will occur either in the PI's stroke rehabilitation research laboratory (College of Health Professions, [name]). The e-learning intervention will occur via a MoodleCE online learning platform.

**Duration of Subjects' Participation:** After enrollment, subjects will participate in a 3-month e-learning + in-clinic stroke rehabilitation program. Subjects will complete a follow up assessment ~60 days after the end of the 3-month program. Thus, subjects will be involved with this study for 5 months.

**Audio and Video Recording:**

- Audio Recording: Each subject will participate in 3 focus groups; one at baseline, immediately following the end of the 5-month intervention, and at the post-intervention follow up. The purpose of the focus groups will be to understand the participants' experiences with regards to the feasibility of the program and changes in his/her self-management skills. Each focus group will be audio recorded. The audio recording will be transcribed. The transcription will be analyzed using qualitative data analyses techniques to ascertain thematic data.
- Video Recording: Subjects will be video recorded during administration of two arm movement tests: the Fugl Meyer Assessment of the Upper Extremity and Wolf Motor Function Test. Trained assessment raters who are blind to testing time point will score the assessments from the video tapes. All videos will be stored on secured, password protected servers behind the MUSC firewall. The procedure for training raters and scoring from videos was developed in the PIs research laboratory and has been used in past and ongoing stroke rehabilitation research clinical trials. Of note- the only people having access to the videos are laboratory personnel who have been approved by the IRB to be part of this study, and who have completed all required IRB privacy and university training.

**Primary and Secondary outcome measures** are identified in the schedule of events table below.

Measurement Construct	Assessment method	Baseline (E1)	Mid (E2)	Post (E3)	Follow up (E4)
SA1: Primary Endpoint: Feasibility					
Health Literacy	Short Assessment of Health Literacy	X		X	
Tech Literacy	Technology Literacy self-evaluation	X		X	
Participants' experiences	Qualitative (focus group)	X		X	
SA2: Secondary Outcomes: Initial efficacy in the following areas:					
SA2a. Effect on self-confidence and social-support					
Self-Efficacy	PROMIS Self-Efficacy for Managing Daily Activities assessment	X		X	X
Social Isolation	PROMIS Social Isolation assessment	X		X	X
Emotional Support	PROMIS Emotional support assessment	X		X	X
SA2b. Effect on self-management skills					
Self-Management Skills	Qualitative (focus group)	X		X	X
SA2c. Effect on arm movement abilities					
Arm movement Impairment	Fugl-Meyer Assessment of the Upper Extremity (FMA-UE)	X	X	X	X
Arm motor function	Wolf Motor Function Test (WMFT)	X	X	X	X
Paretic arm use in the home	Wrist Worn Accelerometry	X	X	X	X
Difficulty using the paretic arm	Stroke Impact Scale – Hand subsection (SIS-H)	X	X	X	X

### **Procedures to lessen the probability or magnitude of risks:**

- Possible risk: Pain and/or Fatigue during stroke rehabilitation therapy.
  - Therapy sessions will be conducted by a licensed occupational therapist. Heart rate and blood pressure will be recorded before, during and after each session and the study therapist will closely monitor the subject for possible pain or fatigue. Subjects will complete pain and fatigue rating scales at the start, middle and end of each therapy session. If pain and/or fatigue ratings exceed minimal (e.g., greater than 4 on a 0-10 rating scale), the therapy session will be stopped, and the subject provided a rest period. If needed, the session will be rescheduled. In previous work we demonstrated that the functional tasks practiced in a session were at a difficulty level that matched or slightly exceeded the subjects' movement ability level, therefore we do not expect that the patient will show movement compensations (movement compensations are known to cause pain and fatigue). To further assure that movement compensations do not emerge and cause pain or fatigue, aspects of each task such as object weight, speed of performance or surface heights will be manipulated by the therapist.
- Possible risk: Embarrassment during the online learning course
  - Subjects enrolled in this study will participate in an online learning course. Other stroke survivors will also be enrolled at the same time. Learning activities will include peer-to-peer asynchronous discussions via the forums, and synchronous discussions via the WebEx Collaborate virtual classroom. It is possible that a subject may feel embarrassed during these discussions. To lessen the probability of embarrassment, subjects will be given the option of choosing a username. If desired, the username can be one that does not reveal the subjects' name. In this way, he/she can remain anonymous during discussion posts. Also, the "guidelines and expectations" for the course (a document posted and reviewed during the first week) will clearly specify that a subject has a choice whether to reveal personal details during peer-to-peer discussions during virtual classroom sessions. This expectation will be repeated before each virtual classroom session.
- Possible risk: Loss of privacy due to the focus groups. A focus group is a discussion group and therefore it is possible that a stroke survivor may reveal information about him/herself during the discussion. This information may cause embarrassment. It is also possible that a focus group member inadvertently shares information outside the focus group. The focus group leader will remind members of this possible risk, that participation is voluntary, and to respect each other's privacy.

**Source Records:** All data about subjects will be collected from the subjects themselves. No other medical records will be accessed in this study.

**Data Collection Procedures:** Subjects will be assessed by trained evaluators who will be members of the study team. The following constructs will be measured by the following methods:

- Short Assessment of Health Literacy is an 18-item test designed to assess an adult's ability to read and understand common medical terms. It will be administered by the

study therapist in a standardized manner. Subjects' receive 1 point for each correct item. A score below 14/18 indicates poor health literacy.

- Technology Literacy self-evaluation is a 23-item questionnaire in which the subject answers true/false to questions about his/her readiness to participate in an online course. Any items in which the subject answers "false" will be reviewed with the subject by the study team in efforts to remedy the lack of technological confidence or literacy.
- Participants' Experiences and Participants' Self-Management Skills: Participants' viewpoints on the course will be assessed qualitatively using focus groups. A focus group guide will structure these sessions. The focus groups will be led by the co-I, [name] who is an experience focus group leader and has the necessary expertise for qualitative data analyses.
- Self-Efficacy will be assessed using the NIH PROMIS Self-Efficacy for Managing Daily Activities assessment. This is an 8-item assessment where a participant reports his/her level of confidence in doing 8 daily activities such as performing household chores, lift/carry groceries and shop/run errands.
- Social Isolation will be assessed using the NIH PROMIS Social Isolation assessment. This is an 8-item patient self-report assessment indicating patients' frequency (never, rarely, sometimes, usually, always) having feelings such as being left out, detached, isolated etc.
- Emotional Support will be assessed using the NIH PROMIS Emotional Support assessment. This 8-item assessment records patient's self-reported view of the frequency (never, rarely, sometimes, usually, always) with which he/she has emotional support from others in areas such as listening, someone to confide it, someone who understands one's problems etc.
- Arm movement impairment will be measured with the Fug-Meyer Assessment of the Upper Extremity, a 30-item assessment that indicates how well a stroke survivor is able to move his/her paretic arm into/out of various postures. Each assessment item is scored on a 3 point ordinal scale (0=unable, 1=partial ability, 2=near normal ability), and the item ratings are totaled and reported out of 60 points so that higher scores indicate less impairment (i.e., more ability).
- Arm motor function will be measured with the Wolf Motor Function Test (WMFT), a 15-item assessment indicating the speed at which a stroke survivor can move the paretic arm to complete functional tasks such as stacking checkers or picking up a soda can. Each assessment item is timed, and the average time per item is reported in seconds so that lower scores indicate greater functional ability.
- Paretic arm use in the home will be measured with wrist worn accelerometers. Subjects will be issued 2 accelerometers which are worn on each wrist for 48 hrs. They are the size of an Apple Watch. Subjects will either bring the devices back to the research center at their next visit or mail them back in mailers that we will provide (we pay postage). 3-D acceleration data will be downloaded and used to calculate variables that indicate the acceleration of the paretic arm relative to the non-paretic arm. A neurologically healthy

individual will have values close to 1 to indicate bimanual arm use, smaller numbers indicate less use of the paretic arm, i.e., over-reliance on the non-paretic arm.

- Difficulty using the paretic arm during daily activities will be assessed with the Stroke Impact Scale – Hand subtest. This is a 5-item assessment in which the patient reports the amount of difficulty using the paretic hand along an ordinal scale (0=no difficulty, 5=great difficulty).

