## 1.0 Objectives / Specific Aims

Our central premise is that survivors must engage in more in-home paretic arm use and less non-paretic arm use because real world use drives neural plasticity more than the limited therapy visits available. We argue that survivors do not use the paretic arm outside of the clinic to maximize beneficial plasticity because post-discharge support from the rehabilitation team is limited, thus survivors do not fully understand why or how to use the paretic arm at home. Although current in/outpatient rehabilitation provides basic education about stroke and managing impairments, current rehabilitation practice does little to empower stroke survivors with knowledge or skills; specifically, knowledge of the neurobiological processes causing the impairment and the requisite skills to manage their own long-term recovery. Our unique interprofessional research team, comprised of experienced stroke rehabilitation providers and a nurse scientist, are award-winning educators and passionately believe that survivors can improve outcomes if supported with knowledge and skills.

Hence, we created a first of its kind multimodal therapy + e-learning program called **Training to Empower Activity-dependent-plasticity-based Arm-use-habits in the Community and at Home** (TEAAC). Here we test its implementation:

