### **SA2: Determine the initial efficacy of TEAAC:**

Early indication of efficacy will be determined by TEAAC-related changes in measures of (1) self-confidence and social support, (2) self-management skills, and (3) paretic arm impairment and at-home paretic arm use. Changes scores will be calculated to detect a treatment effect measured from baseline (pre-TEAAC) to post TEAAC (3 months), and at 5-months to assess retention.

Impact: This project addresses a critical gap in the field because it innovatively addresses survivors' skills needed to be the self-managers of their own recovery for the long term. TEAAC has an online platform which means that it could be immediately incorporated into clinical practice, modules could be added to meet other needs such as ongoing wellness education, or it could easily be redesigned to meet similar needs in other patient populations.

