### 3.0 Intervention to be studied (if applicable)

The **3-month** intervention studied is called **Training to Empower Activity-dependent-plasticity-based Arm-use-habits in the Community and at Home (TEAAC)**. TEAAC has two components: An Online Educational Course and an In-Clinic Rehabilitation Therapy Program.

The TEAAC design and testing timepoints are indicated in the **figure to the left**. Subjects will be tested (see below) at enrollment (Baseline, evaluation timepoint 1, E1)), at the midpoint of the therapy + online program (1.5 months, E2), immediately following the in-clinic therapy + online program (3 months, E3), and 2 months after the program for follow up (5 months, E4).

**TEAAC e-learning:** 3-months of online educational modules include neuroscience education (based on an effective pain educational model) to improve patient self-efficacy, and strategy-training to improve patients' problem-solving abilities for at-home arm use. The course is live on the MUSC MoodleCE platform.

**TEAAC in-clinic therapy:** 24 in-clinic sessions; 3 times/week for 4 weeks (month 1), 2 times/week for 4 weeks (month 2) and 1 time/week for 4 weeks (month 3) with 200 movement repetitions per session. In our RCTs, this therapy dose required ~1.0-1.5 hours/session. A critical element of TEAAC is the focus on linking in-clinic therapy to out-of-clinic real world paretic arm use via MoodleCE Learning Activities.

	month 1	month 2	month 3	month 4	month 5	month 6	month 7	month 8	month 9	month 10	month 11	month 12
N=12	TEAAC Group 1 (n=4)		TEAAC Group 2 (n=4)			TEAAC Group 3 (n=4)		Group1 f/u tests		Group2 f/u tests		Group3 f/u tests

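### Home use of the paretic arm is measured only relative to the other arm, so the result cannot show which arm changed; each arm's own activity should be reported too

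*Combined protocol and SAP*

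**What the plan says.** Section 1.0 states a premise with two parts: "survivors must engage in more in-home paretic arm use and less non-paretic arm use". SA2 then lists "paretic arm impairment and at-home paretic arm use" among the domains in which early efficacy is sought. Change scores run from baseline to 3 months, with a 5-month assessment of retention.

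The schedule of events in Section 10.0 assigns home use of the paretic arm to accelerometry at E1, E2, E3 and E4. Under Data Collection Procedures, "Paretic arm use in the home will be measured with wrist worn accelerometers". Two devices are "worn on each wrist for 48 hrs", and the data are "used to calculate variables that indicate the acceleration of the paretic arm relative to the non-paretic arm". The plan interprets the result as follows: "smaller numbers indicate less use of the paretic arm, i.e., over-reliance on the non-paretic arm". It names no variable for the activity of one arm alone.

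Section 3.0 places E2 at 1.5 months, while therapy is running. In month 2 there are two sessions a week, each of 200 repetitions and about 1.0 to 1.5 hours. On returning the devices, the plan says: "Subjects will either bring the devices back to the research center at their next visit", or they are mailed. It does not say whether the wear period may include a clinic session.

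**The concern.** The outcome is labelled as the amount of use of one arm, but the planned variables compare two arms. A comparison of this kind can rise because the paretic arm does more, because the other arm does less, or through some mix of the two. The plan reads it as paretic use.

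The distinction matters in this trial. Less non-paretic use is itself a target, and Table 2 addresses it directly: Unit C covers the link between using the better arm and recovery of the weaker one, and a Unit E classroom session sets non-paretic against paretic use. A smaller denominator is therefore a possible effect of the program. The rationale in Section 2.0 (A.5) also concerns the amount of paretic movement, which it says therapy alone does not supply. A ratio carries no information on amount. The study has one cohort and no comparison group, so within-subject change is all the efficacy evidence there will be. At stake is whether the pilot can say that survivors used the paretic arm more at home.

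A smaller worry concerns E2. If a supervised session falls within the 48 hours, an outcome described as home use contains clinic movement.

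**Working it through.** **The plan's own figures.** The documents give no accelerometry values, so there is none to reproduce. The one stated figure that bears on the E2 point is the session count: 3×4 + 2×4 + 1×4 = 24, which agrees with Section 3.0. With months of 4 weeks, 1.5 months is week 6, inside the twice-weekly block (weeks 5 to 8).

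**What the ratio can identify.** The plan does not give the formula. I take the simplest form, R = P/N, where P is paretic and N is non-paretic activity over the 48 hours.

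- If P is fixed and N falls by a fraction f, R is multiplied by 1/(1 − f).
- If N is fixed and P rises by a fraction g, R is multiplied by 1 + g.
- The two cases give the same R when g = f/(1 − f). For f = 0.20, g = 0.20/0.80 = 0.25.

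| Change in paretic use | Change in non-paretic use | Multiplier of R | Change in R |
|---|---|---|---|
| none | −10% | 1/0.90 | +11.1% |
| none | −20% | 1/0.80 | +25.0% |
| none | −30% | 1/0.70 | +42.9% |
| +25% | none | 1.25 | +25.0% |
| −10% | −20% | 0.90/0.80 | +12.5% |
| +20% | +20% | 1.20/1.20 | 0% |

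The second and fourth rows cannot be told apart. In the fifth row R rises although paretic use has fallen. In the last row a real gain in paretic use leaves no trace. Any variable that depends on the two arms only through their ratio has the same limitation.

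**Whether another outcome fills the gap.** The Fugl-Meyer and Wolf tests are administered and video-scored, so they measure ability under test. The Stroke Impact Scale hand items are self-reported difficulty. None measures how much the arm is used at home.

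**E2.** One session is 1.0/48 = 2.1% to 1.5/48 = 3.1% of the wear period. Its effect on R, if it falls inside, depends on values that the plan does not give. For illustration, assume 32 waking hours, N = 16 h, P = 4 to 12 h, a session of h hours with the paretic arm active throughout, and the other arm active for a share u of the session:

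R′ = [P(32 − h)/32 + h] / [N(32 − h)/32 + h·u]

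- Low end (P = 12, h = 1.0, u = 1): 12.625/16.5 = 0.765 against 0.75, or +2%.
- High end (P = 4, h = 1.5, u = 0): 5.3125/15.25 = 0.348 against 0.25, or +39%.

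The range is wide because the inputs are unknown. It shows that a session could matter, not that it will.

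**The case against.** The strongest reply is that a relative measure suits the theory. Section 2.0 treats over-reliance on the non-paretic arm as the harmful behavior, and the plan describes low values in those words. A rise brought about by less non-paretic use is then partly a change that the program wants. A ratio also cancels differences between visits in overall activity or in wear time when both wrists are affected alike. All of this stands, and it is why the ratio should stay. It does not rescue the reading of the ratio as paretic use, because it concedes that two targets are combined in one number.

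It can also be said that a large fall in non-paretic use without any substitution is not shown to be likely. The documents describe no restraint or quota for that arm, and most of the training is directed at the paretic arm. That is fair, and the percentages above are illustrations rather than predictions.

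On E2, a reader might calculate a chance of overlap. A 48-hour window placed at random in a 168-hour week, with two sessions at least 48 hours apart, gives 2×48/168 = 57%, and one might contrast this with no overlap at the other evaluations. The documents support neither figure. They do not say that wear starts at random. Under the same spacing, a wear period that begins as the subject leaves a session contains no further session. Nor do they say how soon after E1 therapy begins, so a clean baseline is not established either. What stands is only that overlap at E2 is not excluded.

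Finally, this is one of several secondary outcomes in a descriptive study of 12 subjects, and the raw data would allow a separate-arm analysis later. That limits the weight of the point. It is also the reason that the change costs so little now.

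**Conclusion.** The point holds in a limited form. As planned, the accelerometry result can show that the balance between the arms moved, but not which arm moved it. A 20% fall in non-paretic use alone looks the same as a 25% rise in paretic use, and an equal rise in both arms is invisible. The direction of this conclusion follows from the plan's description of the variables. The sizes assume a simple ratio and invented changes.

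A reader might go further and infer that the ratio is an invalid outcome, or that any rise driven by the non-paretic arm is a false positive. The documents do not support that, since less non-paretic use is part of the stated premise. A reader might also infer that a value near 1 could simply mean two idle arms. That depends on an algorithm that the plan does not give, and the plan offers values close to 1 as the pattern of a healthy person.

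The E2 matter is secondary. It concerns one point on the descriptive plots planned in Section 12.0. The SA2 change scores, taken at 3 and 5 months, do not use the E2 value. The primary feasibility outcome and the sample size are untouched by either issue.

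**What to change.** In Section 10.0, Data Collection Procedures, keep the relative variables and add each arm's own activity over the 48 hours, paretic and non-paretic separately, at E1 to E4. Hours of movement or summed activity would serve. State the formula for each variable and report the hours worn, since a single-arm total depends on wear time more than a ratio does. Base any statement about paretic arm use at home on the paretic-arm value, and use the ratio to describe the balance between the arms.

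Add one sentence on clinic time at E2: either schedule the 48 hours between sessions, or log the session times and remove them before calculating. Wording it to cover every wear period would settle the timing at E1 as well.

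No new data collection is needed, because both wrists are already recorded. The cost is a few lines of analysis and a scheduling or session-time note.
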